This is a single arm multi-centric non-randomized (prospective) clinical trial. The study will be divided in two parts. The first one will aim at quantifying the HIV reservoir in a large group of patients under ART with strictly predefined inclusion and exclusion criteria. The second step encompasses an analytical treatment interruption among participants with the lowest viral reservoir.

2.2. Study objectives and Hypotheses

Primary Objective

The primary objective is to determine the proportion of post treatment controllers (PTC) (i.e. patients under cART with low baseline peripheral blood proviral DNA that will show sustained viral suppression at 48 weeks post treatment interruption (TI).

Secondary Objectives

a. To confirm the safety of a TI strategy in selected HIV patients

b. To assess the viral reservoir magnitude prior, during and after TI

c. To assess the viral and host dynamics in those participants with viral rebound post TI.

Exploratory Objective

- a. The identification of predictors (clinical and/or laboratory) of PTC phenotype.
- b. The identification of predictors for viral rebound over time.

2.3. Variables of interest

Primary: The proportion of participants with plasma viral load (pVL) below the lower limit of detection (< 50 HIV RNA copies/ml plasma) 48 weeks following interruption of ART.

Secondary:

- The numbers and percentages of AE's and SAE's during the whole study period.
- Viral reservoir (total HIV-1 DNA) and viral transcription (total HIV-1 cellassociated RNA) measurements at every visit between baseline (just before TI) until viral rebound and 12 weeks after viral rebound.
- Repeated pVL measurements.

Exploratory: Potential clinical and/or laboratory variables, such as demographic and epidemiological data, medical history (past and current), vital parameters, ultrasensitive HIV viral load, CD4 T cell count and laboratory test data (e.g. hemoglobin, ANC, platelets, creatinine, AST & ALT), viral reservoir (quantitative viral outgrowth measurement) and viral release measurements (spontaneous and stimulated) at baseline.

3. Description of study population

3.1. Analysis populations

The statistical analyses will be performed on all participants enrolled in the study and who met all inclusion and exclusion criteria. Complete case analysis will be performed for all statistical analyses.

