3.2. Patient accounting

The numbers of participants screened, enrolled and excluded will be presented. Excluded participants will be summarized by reason for exclusion in a CONSORT flow diagram by the PI.

All patients who conform to all inclusion and exclusion criteria and are enrolled into the study will be tabulated. The number of patients discontinued will be tabulated by reason for study discontinuation (Completed the study, Lost to Follow Up, Withdrawal of Consent, Discontinuation of drug for Safety or Other Reasons, Death, Other) (Example Table 1). This information will also be described separately in a CONSORT flow diagram.

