4.1. Primary Objective

The primary objective will be assessed by estimating the proportion of participants with undetectable viral load (<50 HIV RNA copies/ml plasma) 48 weeks after interruption of ART. A 95% CI for the proportion will be calculated using Wilson's score method (Example Table 3). Respective proportions at different time points (week 2, 4, 6 and 8) will be also calculated for descriptive purposes.

4.2. Secondary Objectives

Adverse events (AEs) will be coded using the Medical Dictionary for Regulatory Activities (MEDDRA) and will be reported based on MEDDRA preferred terms and body systems. All AEs will be analyzed based on counts of patients with a specific category and not on counts of individual adverse events. The relationship between AEs and ARV interruption is determined by the investigator and categorized as "drugrelated" if unlikely, possibly, likely or definitely related to treatment interruption. All AEs definitely unrelated to intervention will also be used to examine the relationship between AEs and intervention.

All AEs and all serious AEs from the beginning of treatment interruption until the end of the study (end of follow-up period) are reported. AE counts will be summarized for the whole study period (treatment interruption and follow-up period). Counts (%) of patients with AEs, drug-related AEs and serious AEs will be presented by Meddra body system and preferred term together with a 95% Wilson confidence interval (Example Table 4 and 5).

Reservoir replenishment and HIV viral load kinetics following ART interruption will be summarized in terms of medians and interquartile ranges (Example Table 3). No formal statistical testing will be done in these results. If present, pVL rebound will be represented graphically with a spaghetti plot. Furthermore, the measurements over time of viral load rebound and viral reservoir will be presented graphically for every patient included in the study (one line for every patient over time).

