4.3. Exploratory Objective

Potential predictors of post-treatment control (end of second part of the study) will be assessed by Fisher's exact test at 5% significance level (Example Table 6). The time to viral rebound will be assessed by survival analysis methodology, e.g. Kaplan-Meier estimates and curves (Example table 7). Potential predictors of viral rebound will be examined by single Cox regression models (Example Table 8).

4.4. Subgroup Analysis

No subgroup analyses will be performed in this study due to the small sample size .

5. Example Tables and Figures

Example Table 1: Patient Accounting

	n (%)
Screened	ХХ
Excluded	xx (xx %)
[add reason for exclusion]	xx (xx %)
	xx (xx %)
Enrolled to the first stage	xx (xx %)
- Completed the study	xx (xx %)
- Early withdrawals	xx (xx %)
- Lost to follow-up	xx (xx %)
- Consent withdrawal	xx (xx %)
Excluded from second stage	
Enrolled to the second stage	xx (xx %)
- Completed the study	xx (xx %)
- Early withdrawals	xx (xx %)
- Lost to follow-up	xx (xx %)
- Consent withdrawal	xx (xx %)

Example Table 2: Baseline Characteristics at Recruitment

	n (%)
Ν	XX
Epidemiological findings	
Age (yr): median (IQR)	xx (xx - xx)
Gender: male (%)	xx (xx)
female (%)	xx (xx)
Ethnicity: [add ethnic categories]	
Transmission route: [add categories]	
Duration of HIV infection (months/years): median (IQR)	
Total duration of antiviral treatment (months): median (IQR)	
Clinical findings	
Last antiviral treatment: PI+ NRTI	xx (xx)
NNRTI+NRTI	xx (xx)
II+ NRTI	xx (xx)
other	xx (xx)

xx (xx - xx)
xx (xx - xx)

Example Table 3: Summary of Primary and Secondary Analysis Results

	n/N (%, 95% Cl)
Primary analysis	
Number of participants with undetectable viral load (<50 HIV	xx/xxx
RNA copies/ml plasma) 48 weeks after interruption of ART	(xx; xx - xx)
Number of participants with undetectable viral load (<50 HIV RNA copies/ml plasma) at week:	
- 2	xx/xxx
	(xx; xx - xx)
- 4	xx/xxx
	(xx; xx - xx)
- 6	xx/xxx
	(xx; xx - xx)
- 8	xx/xxx
	(xx; xx - xx)
Secondary analysis	
Viral Reservoir at baseline (/10*6 PBMC's): median (IQR)	xx (xx - xx)
Viral Reservoir after TI (/10*6 PBMC's): median (IQR)	xx (xx - xx)
Viral load rebound by week (in copies/ml plasma): median (IQR)	
- 0 (baseline)	xx (xx - xx)
- 2	xx (xx - xx)
- 4	xx (xx - xx)
- 8	xx (xx - xx)

Example Table 4: Counts of patients (%) with Adverse Events by Body System and Preferred Term (Meddra)

	(N=xx) n(%)
Blood and Lymphatic System	xx (xx)
Anaemia	xx (xx)

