Gastrointestinal Disorders	xx (xx)
Diarrhoea	xx (xx)
	xx (xx)

Note: similar tables will be presented for drug-related AEs, serious AEs, and serious drug-related AEs.

Example Table 5: Counts of patients (%) with Adverse Events by causality classification

Number of patients (%; 95% Cl) with:	(N=xx)
- any adverse event	xx (xx; xx - xx)
- any intervention-related adverse event	xx (xx; xx - xx)
- any serious adverse event	xx (xx; xx - xx)
- any intervention-related serious adverse event	xx (xx; xx - xx)

Example Table 6: Exploratory analysis of potential predictors of post-treatment control (PTC)

Characteristic	Levels	PTC = Yes n(%)	PTC = No n(%)	OR (95% CI)	p - value
Age (years)	< 30	xx (xx)	xx (xx)	1 (ref)	ХХ
	30 – 40	xx (xx)	xx (xx)	xx (xx - xx)	
	> 40	xx (xx)	xx (xx)	xx (xx - xx)	
Gender	Male	xx (xx)	xx (xx)	1 (ref)	xx
	Female	xx (xx)	xx (xx)	xx (xx - xx)	xx
HIV viral load		xx (xx - xx)	xx (xx - xx)	xx (xx - xx)	xx
CD4 T cell count		xx (xx - xx)	xx (xx - xx)	xx (xx - xx)	xx
Hemoglobin		xx (xx - xx)	xx (xx - xx)	xx (xx - xx)	xx
ACN		xx (xx - xx)	xx (xx - xx)	xx (xx - xx)	xx
platelets		xx (xx - xx)	xx (xx - xx)	xx (xx - xx)	xx
Creatinine		xx (xx - xx)	xx (xx - xx)	xx (xx - xx)	xx
AST		xx (xx - xx)	xx (xx - xx)	xx (xx - xx)	xx
ALT		xx (xx - xx)	xx (xx - xx)	xx (xx - xx)	ХХ
Viral reservoir at baseline		xx (xx - xx)	xx (xx - xx)	xx (xx - xx)	ХХ
Viral outgrowth at baseline		xx (xx - xx)	xx (xx - xx)	xx (xx - xx)	ХХ

	Week 2		Week 4		Week 6		Week 8	
	n failed/	Probability viral						
	n censored	suppression (95 % CI)						
All	xx/xx	xx (xx - xx)						
Subset analysis								
	xx/xx	xx (xx - xx)						
	xx/xx	xx (xx - xx)						

Example Table 7: Kaplan-Meier estimates for time until viral load rebound

Example Table 8: Exploratory analysis of potential predictors of viral rebound

Predictor	Levels	Hazard ratio (95% CI)	p-value
Age (years)	< 30	1 (ref)	хх
	30 – 40	xx (xx - xx)	ХХ
	> 40	xx (xx - xx)	ХХ
Gender	Male	1 (ref)	ХХ
	Female	xx (xx - xx)	ХХ
HIV viral load		xx (xx - xx)	ХХ
CD4 T cell count		xx (xx - xx)	ХХ
Hemoglobin		xx (xx - xx)	ХХ
ACN		xx (xx - xx)	ХХ
platelets		xx (xx - xx)	ХХ
Creatinine		xx (xx - xx)	ХХ
AST		xx (xx - xx)	ХХ
ALT		xx (xx - xx)	ХХ
Viral reservoir at baseline		xx (xx - xx)	XX
Viral outgrowth at baseline		xx (xx - xx)	ХХ

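### Read literally, the complete-case rule removes participants stopped for high viral load from the later by-week rows of Example Table 3, which would then overstate suppression

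*SAP*

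**What the plan says.** **Analysis rule.** SAP 3.1 analyses all enrolled participants who met the eligibility criteria and states: "Complete case analysis will be performed for all statistical analyses". Protocol 8.3.6 has the same rule. Neither makes an exception for people who restart cART.

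**Rows affected.** SAP 4.1 estimates the week-48 proportion below 50 copies/ml and adds: "Respective proportions at different time points (week 2, 4, 6 and 8) will be also calculated for descriptive purposes". Example Table 3 prints these as n/N without defining N. For the medians, SAP 4.2 says "Reservoir replenishment and HIV viral load kinetics following ART interruption will be summarized in terms of medians and interquartile ranges (Example Table 3". The block headed "Viral load rebound by week (in copies/ml plasma): median (IQR" shows weeks 0, 2, 4 and 8, with no N and no week 6. Week 6 therefore appears only in the proportion rows, and week 8 in both.

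**Stopping.** Under Protocol 5.1.7, pVL above 1,000 at two consecutive time points at least 3 days apart, or a single value above 10,000, leads to an End of Study visit and a cART restart. Protocol 5.1.6 places the last study visit at week 48 or at rebound, and 5.1.8 starts the post-intervention phase at re-initiation. Protocol 4.5 lists rebound-based restart among the withdrawal reasons. Protocol 11.1 expects rebound in most participants.

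**Rebound as an event.** SAP 4.3 says "The time to viral rebound will be assessed by survival analysis methodology, e.g. Kaplan-Meier estimates and curves (Example table 7", and the shell is "Example Table 7: Kaplan-Meier estimates for time until viral load rebound". SAP 2.3 also bounds the reservoir data by rebound: "measurements at every visit between baseline (just before TI) until viral rebound and 12 weeks after viral rebound". No section gives a threshold or a date for this event.

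**The concern.** A participant stopped on pVL is missing from later off-cART visits because the virus came back. Removing that person takes a known non-suppressed case out of the denominator and nothing out of the numerator, so the percentage below 50 can only rise. In the same way, the median pVL loses its highest contributors.

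Rebound kinetics is the third secondary endpoint (Protocol 3.2), and these rows print in the same table as the primary result of a functional-cure study. A reader could take the week-6 and week-8 figures as describing the cohort that interrupted treatment, when they describe only those not yet stopped. The Kaplan-Meier table covers the same weeks but needs an event definition before it can serve as a cross-check.

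**Working it through.** **1. The plan's own figure.** Protocol 8.4 gives Wilson interval widths of 18 to 25 points for 32 participants and 5% to 15% control; Protocol 4.3 translates this to 2 to 5 controllers. With z = 1.96, the Wilson interval is

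(p + z²/2n ± z·√[p(1−p)/n + z²/4n²]) / (1 + z²/n).

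- 2/32: 1.7% to 20.1%, width 18.4.
- 5/32: 6.9% to 31.8%, width 24.9.

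The stated widths reproduce, with all 32 in the denominator.

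**2. When a pVL stop can remove someone.** Visits fall at weeks 2, 4, 6 and 8.

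- Week 2: there is no earlier scheduled off-cART value, so scheduled visits cannot remove anyone.
- Week 4: removal needs a week-2 value above 10,000, or one above 1,000 that is confirmed before week 4.
- Weeks 6 and 8: two consecutive scheduled values above 1,000, or a single one above 10,000, are enough.

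The later rows are therefore the main concern.

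**3. Proportions.** Let N interrupt ART, s of them stop earlier on pVL, and x be below 50 at the visit. The share of all who interrupted is x/N; the complete-case share is x/(N − s). The ratio is N/(N − s). The documents give no s by week, so x and s are assumptions, here with no other exits.

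| Week 8, x = 8, N = 32 | n/N | % | 95% Wilson |
|---|---|---|---|
| All who interrupted | 8/32 | 25.0 | 13.3 to 42.1 |
| 8 stopped and dropped | 8/24 | 33.3 | 18.0 to 53.3 |
| 16 stopped and dropped | 8/16 | 50.0 | 28.0 to 72.0 |

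**4. Week 48 under the same rule.** With 2 controllers, 2/32 = 6.3% (1.7 to 20.1). If 27 had stopped and were dropped (assumed), 2/5 = 40.0% (11.8 to 76.9).

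**5. Week-8 median (assumed values).** Suppose 8 have stopped. Of the 24 observed, 5 are below 50 and 19 are evenly spaced from 100 to 5,000, a step of 4,900/18 = 272.2.

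- Observed only: the mean of positions 12 and 13 of 24 is (1,733 + 2,006)/2, about 1,869.
- Stops ranked highest: the mean of positions 16 and 17 of 32 is (2,822 + 3,094)/2 = 2,958.

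**6. Other exits can act the other way.** Suppose 16 of 32 are below 50, 4 of those leave for non-virological reasons, and nobody stops on pVL. Complete case gives 12/28 = 42.9%. Had they stayed it would be 16/32 = 50.0%. Counting them as not suppressed gives 12/32 = 37.5%.

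**The case against.** The strongest reply is that nobody need read the plan this way. The SAP population is all enrolled participants who met the criteria. Protocol 5.1.8 sorts people into controllers and those with rebound, Example Table 6 has a column for non-controllers, and Protocol 8.4 computes precision on 32. Someone stopped on pVL has a known outcome and is not obviously an incomplete case. This stands as a reason not to claim that the bias will occur. It does not supply the missing rule: the only one written is complete case, for all analyses.

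The by-week proportions are labelled descriptive, and no testing is planned for the kinetics summaries. Example Table 7 gives Kaplan-Meier suppression probabilities at weeks 2, 4, 6 and 8 with failed and censored counts, and SAP 4.2 plots a line per patient. This lowers the stakes. These displays can reveal the loss, but they do not correct the percentages or the median, and the Kaplan-Meier table depends on the undefined event.

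A reader might infer more:

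- *The primary result will be inflated.* The rule reaches the week-48 row, but the indications above point to all 32 as the intended denominator, so the documents do not establish this.
- *Every departure from follow-up inflates suppression.* This holds only for pVL stops; step 6 shows the reverse for other exits.
- *The plan contains rival definitions of rebound.* The 400 copies/ml threshold in Protocol 1.1 describes a cited cohort. Within the trial, rebound is linked to restart, but no analysis event or date is set.
- *Disposition would be lost.* SAP 3.2 lists "Completed the study, Lost to Follow Up, Withdrawal of Consent, Discontinuation of drug for Safety or Other Reasons, Death, Other". A pVL stop can be recorded under the last category; it would just not be visible separately.

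**Conclusion.** The point holds in a limited form. The written complete-case rule, applied literally together with the pVL stopping rule, makes the later by-week rows describe only those not yet stopped on pVL, and those rows would overstate suppression. The rows are descriptive, the reading is not forced, and the upward direction applies to virological stops only.

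The size is set by how many have stopped: the percentage is multiplied by 32/24 = 1.33 with 8 stops and by 32/16 = 2 with 16. These counts, and the 8 suppressed participants, are assumptions; only the 32 and the expectation of rebound in most participants come from the Protocol. Week 2 is essentially untouched and week 4 is less exposed.

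It merits a change to the SAP because a stated rule, followed as written, would give a biased figure, and the remedy uses data already collected.

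**What to change.** In the SAP:

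1. Exempt the proportion-below-50 rows, including week 48, from the complete-case rule. Take all participants who interrupted ART as N, use off-cART values only, and count anyone stopped earlier on a pVL criterion as not below 50 at all later weeks.
2. Within that N, show non-virological exits and missed visits as a separate count. Take the main percentage with that count set aside, and add a sensitivity analysis that counts them as not suppressed. In the step 6 example these are 42.9% and 37.5%. Neither recovers the 50.0%, so the separate count must be visible.
3. For the week-8 median, print N and either rank pVL stops highest or label the row as those still off cART.
4. Define the rebound event and its date for Example Tables 7 and 8, for analysis purposes only.

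A pVL-stop line in Example Table 1 would help but is optional. No restart criterion is questioned. Protocol 4.5 and 5.1.9 refer to section 5.1.5 for the restart criteria; that section is the baseline visit and the criteria stand in 5.1.7, so these passages must be reconciled.

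The cost is a few sentences of SAP text, slightly more programming, and possibly less favourable percentages.

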4.3. Exploratory Objective

Potential predictors of post-treatment control (end of second part of the study) will be assessed by Fisher's exact test at 5% significance level (Example Table 6). The time to viral rebound will be assessed by survival analysis methodology, e.g. Kaplan-Meier estimates and curves (Example table 7). Potential predictors of viral rebound will be examined by single Cox regression models (Example Table 8).

4.4. Subgroup Analysis

No subgroup analyses will be performed in this study due to the small sample size .

5. Example Tables and Figures

Example Table 1: Patient Accounting

	n (%)
Screened	ХХ
Excluded	xx (xx %)
[add reason for exclusion]	xx (xx %)
	xx (xx %)
Enrolled to the first stage	xx (xx %)
- Completed the study	xx (xx %)
- Early withdrawals	xx (xx %)
- Lost to follow-up	xx (xx %)
- Consent withdrawal	xx (xx %)
Excluded from second stage	
Enrolled to the second stage	xx (xx %)
- Completed the study	xx (xx %)
- Early withdrawals	xx (xx %)
- Lost to follow-up	xx (xx %)
- Consent withdrawal	xx (xx %)

Example Table 2: Baseline Characteristics at Recruitment

	n (%)
Ν	XX
Epidemiological findings	
Age (yr): median (IQR)	xx (xx - xx)
Gender: male (%)	xx (xx)
female (%)	xx (xx)
Ethnicity: [add ethnic categories]	
Transmission route: [add categories]	
Duration of HIV infection (months/years): median (IQR)	
Total duration of antiviral treatment (months): median (IQR)	
Clinical findings	
Last antiviral treatment: PI+ NRTI	xx (xx)
NNRTI+NRTI	xx (xx)
II+ NRTI	xx (xx)
other	xx (xx)

xx (xx - xx)
xx (xx - xx)

Example Table 3: Summary of Primary and Secondary Analysis Results

	n/N (%, 95% Cl)
Primary analysis	
Number of participants with undetectable viral load (<50 HIV	xx/xxx
RNA copies/ml plasma) 48 weeks after interruption of ART	(xx; xx - xx)
Number of participants with undetectable viral load (<50 HIV RNA copies/ml plasma) at week:	
- 2	xx/xxx
	(xx; xx - xx)
- 4	xx/xxx
	(xx; xx - xx)
- 6	xx/xxx
	(xx; xx - xx)
- 8	xx/xxx
	(xx; xx - xx)
Secondary analysis	
Viral Reservoir at baseline (/10*6 PBMC's): median (IQR)	xx (xx - xx)
Viral Reservoir after TI (/10*6 PBMC's): median (IQR)	xx (xx - xx)
Viral load rebound by week (in copies/ml plasma): median (IQR)	
- 0 (baseline)	xx (xx - xx)
- 2	xx (xx - xx)
- 4	xx (xx - xx)
- 8	xx (xx - xx)

Example Table 4: Counts of patients (%) with Adverse Events by Body System and Preferred Term (Meddra)

	(N=xx) n(%)
Blood and Lymphatic System	xx (xx)
Anaemia	xx (xx)
Gastrointestinal Disorders	xx (xx)
Diarrhoea	xx (xx)
	xx (xx)

Note: similar tables will be presented for drug-related AEs, serious AEs, and serious drug-related AEs.

Example Table 5: Counts of patients (%) with Adverse Events by causality classification

Number of patients (%; 95% Cl) with:	(N=xx)
- any adverse event	xx (xx; xx - xx)
- any intervention-related adverse event	xx (xx; xx - xx)
- any serious adverse event	xx (xx; xx - xx)
- any intervention-related serious adverse event	xx (xx; xx - xx)

Example Table 6: Exploratory analysis of potential predictors of post-treatment control (PTC)

Characteristic	Levels	PTC = Yes n(%)	PTC = No n(%)	OR (95% CI)	p - value
Age (years)	< 30	xx (xx)	xx (xx)	1 (ref)	ХХ
	30 – 40	xx (xx)	xx (xx)	xx (xx - xx)	
	> 40	xx (xx)	xx (xx)	xx (xx - xx)	
Gender	Male	xx (xx)	xx (xx)	1 (ref)	xx
	Female	xx (xx)	xx (xx)	xx (xx - xx)	xx
HIV viral load		xx (xx - xx)	xx (xx - xx)	xx (xx - xx)	xx
CD4 T cell count		xx (xx - xx)	xx (xx - xx)	xx (xx - xx)	xx
Hemoglobin		xx (xx - xx)	xx (xx - xx)	xx (xx - xx)	xx
ACN		xx (xx - xx)	xx (xx - xx)	xx (xx - xx)	xx
platelets		xx (xx - xx)	xx (xx - xx)	xx (xx - xx)	xx
Creatinine		xx (xx - xx)	xx (xx - xx)	xx (xx - xx)	xx
AST		xx (xx - xx)	xx (xx - xx)	xx (xx - xx)	xx
ALT		xx (xx - xx)	xx (xx - xx)	xx (xx - xx)	ХХ
Viral reservoir at baseline		xx (xx - xx)	xx (xx - xx)	xx (xx - xx)	ХХ
Viral outgrowth at baseline		xx (xx - xx)	xx (xx - xx)	xx (xx - xx)	ХХ

	Week 2		Week 4		Week 6		Week 8	
	n failed/	Probability viral						
	n censored	suppression (95 % CI)						
All	xx/xx	xx (xx - xx)						
Subset analysis								
	xx/xx	xx (xx - xx)						
	xx/xx	xx (xx - xx)						

Example Table 7: Kaplan-Meier estimates for time until viral load rebound

Example Table 8: Exploratory analysis of potential predictors of viral rebound

Predictor	Levels	Hazard ratio (95% CI)	p-value
Age (years)	< 30	1 (ref)	хх
	30 – 40	xx (xx - xx)	ХХ
	> 40	xx (xx - xx)	ХХ
Gender	Male	1 (ref)	ХХ
	Female	xx (xx - xx)	ХХ
HIV viral load		xx (xx - xx)	ХХ
CD4 T cell count		xx (xx - xx)	ХХ
Hemoglobin		xx (xx - xx)	ХХ
ACN		xx (xx - xx)	ХХ
platelets		xx (xx - xx)	ХХ
Creatinine		xx (xx - xx)	ХХ
AST		xx (xx - xx)	ХХ
ALT		xx (xx - xx)	ХХ
Viral reservoir at baseline		xx (xx - xx)	XX
Viral outgrowth at baseline		xx (xx - xx)	ХХ

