### Step 4: Proportion of participants that will qualify for a treatment interruption.

The proportion of screened patient who may qualify for treatment interruption is based on preliminary research data generated in UZ Gent. It is evaluated at 7% of the screened patients corresponding to 45 potential patients to be included in the trial.

**Step 5: Proportion of patients that will accept to undergo a treatment interruption.** Although many patients have manifested their interest in participating into HIV trials, a

conservative and rational drop-out rate of 30% has to be taken into account in this project. Not all participants will be eager to interrupt a longstanding and most probably well supported treatment. On the other hand, the participants at this stage will be very motivated persons as they already underwent a stringent selection procedure (among others interview with psychologist) and heavy procedure (leukapheresis). The estimated number of participants would therefore be reduced to 32.

The proportion of post-treatment controllers is conservatively estimated at 5 to 15%, i.e. 2 to 5 out of the 32 study participants. (Of note this estimate is derived from data of PTC that were not selected based on a low HIV reservoir in contrast to the present study).

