### 8.3.4 Secondary endpoints

Safety of interrupting ART will be evaluated based on AEs and SAEs percentages together with a 95% Wilson confidence interval.

Reservoir replenishment and HIV viral load kinetics following ART interruption will be summarized in terms of medians and interquartile ranges. If present, pVL rebound will be represented graphically with a spaghetti plot.

Potential predictors of post-treatment control will be assessed by Fisher's exact test at 5% significance level.

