### 8.3.6 Multiplicity and Missing Data

Complete-case analyses will be performed.

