3.3. Description of study population

Patients will be described with respect to baseline characteristics for each of the two stages of the study separately. The description will be in terms of medians and interquartile ranges for continuous characteristics and using counts and percentages for categorical characteristics (Example Tables 2). The clinical importance of any imbalance will be noted, though statistical tests of significance will not be undertaken.

4. Statistical Methods

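### Fisher's exact test is the only method named for predictors of post-treatment control, but ten of the twelve rows in SAP Example Table 6 have no categories to run it on

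*SAP*

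**What the plan says.** SAP 4.3 gives one method for predictors of post-treatment control: "Potential predictors of post-treatment control (end of second part of the study) will be assessed by Fisher's exact test at 5% significance level". Protocol 8.3.4 agrees: "Potential predictors of post-treatment control will be assessed by Fisher's exact test at 5% significance level". Neither says whether the test is one- or two-sided.

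SAP 4.3 refers to Example Table 6, which lists twelve characteristics. Age has three levels and gender has two, each with a reference. The other ten are HIV viral load, CD4 count, hemoglobin, neutrophils, platelets, creatinine, AST, ALT, viral reservoir and viral outgrowth. For these the Levels cell is empty. The cells under PTC = Yes and PTC = No hold a value with a range, although both columns are headed n(%). Every row has places for an odds ratio with 95% CI and a p-value.

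Two other places bear on how the ten rows were meant. SAP 3.3 describes participants with "medians and interquartile ranges for continuous characteristics and using counts and percentages for categorical characteristics". Example Table 3 uses the same value-with-range layout for the same variable (its row reads "Viral Reservoir at baseline (/10*6 PBMC's): median (IQR").

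The only regression in SAP 4.3 is for a different outcome: "Potential predictors of viral rebound will be examined by single Cox regression models". The only sentence in protocol 8.3.6, whose title covers multiplicity and missing data, is "Complete-case analyses will be performed". Protocol 4.3 (Step 5) expects few controllers, "i.e. 2 to 5 out of the 32 study participants".

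**The concern.** Fisher's exact test works on a contingency table. Ten of the twelve predictors have no categories, and the cell layout suggests they were to stay continuous. An odds ratio for an uncategorised variable needs a model and a unit of increase, and the plan gives neither. The headings imply counts, the cells imply medians, and the named test fits only the headings.

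The analyst would have to choose cut-points, or another test or model, possibly once the data are visible. With so few controllers the cut decides whether the 5% level can be reached at all. A cut picked for its result also raises the false-positive rate. Viral outgrowth is among the ten rows, and protocol 5.3 singles it out for later evaluation as a predictor of functional cure.

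**Working it through.** **Inputs.** N = 32 (protocol 4.3 and 8.4). Controllers k = 2 to 5 (protocol 4.3, Step 5). Tests are taken as two-sided at 5%, which is an assumption. Cuts are illustrative, because the plan states none. Lists below run over k = 2, 3, 4, 5 unless noted.

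**Step 1: the plan's own figure.** No precision figure is given for the predictor analysis. The only one is the Wilson interval width in protocol 8.4, 18 to 25 percentage points. Width = [2z/(1+z²/n)] × √[p(1−p)/n + z²/(4n²)], with z = 1.96 and n = 32.
- p = 2/32: 3.500 × √(0.00183 + 0.00094) = 18.4 points.
- p = 5/32: 3.500 × √(0.00412 + 0.00094) = 24.9 points.

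The figure reproduces, so 32 participants and 2 to 5 controllers are the right inputs.

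**Step 2: row count.** Twelve characteristics, less age and gender, leaves ten without levels.

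**Step 3: best case for Fisher at a median (16/16) cut.** The smallest two-sided p arises when all controllers fall on one side: p = 2·C(16,k)/C(32,k).

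| k | Arithmetic | Smallest p |
|---|---|---|
| 2 | 2×120/496 | 0.48 |
| 3 | 2×560/4,960 | 0.23 |
| 4 | 2×1,820/35,960 | 0.10 |
| 5 | 2×4,368/201,376 | 0.043 |

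A median cut cannot give p<0.05 with fewer than 5 controllers, however strong the predictor.

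**Step 4: other cuts.** Uneven cuts can reach 5% when all controllers fall in the smaller group.
- k = 2: a 7/25 cut gives C(7,2)/C(32,2) = 21/496 = 0.042, but an 8/24 cut gives 28/496 = 0.056.
- k = 3: 11/21 gives 165/4,960 = 0.033.
- k = 4: 15/17 gives 1,365/35,960 = 0.038.

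With 2 controllers, moving the cut by one participant changes the answer.

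**Step 5: choosing the cut after seeing the data.** For a useless, untied predictor every set of k positions among 32 is equally likely. I counted the sets in which at least one of five cuts (8/24, 11/21, 16/16, 21/11, 24/8) gives p<0.05: 0/496, 330/4,960, 3,012/35,960 and 19,296/201,376. That is 0%, 6.7%, 8.4% and 9.6%. The 0% at k = 2 belongs to those five cuts. Searching every possible cut gives 8.5%, 13.7%, 17.1% and 17.2%.

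**Step 6: exact rank-sum test on the undichotomised value.** Its size by full enumeration, without ties, is 4.8%, 5.0%, 4.7% and 4.6%, and there is no cut to choose. The smallest two-sided p is 2/C(32,k): 2/32 = 0.0625 with 1 controller and 2/496 = 0.004 with 2. The test is therefore useful only from 2 controllers. The chance of 0 or 1 controllers is (1−p)³² + 32p(1−p)³¹, which is 52%, 16% and 4% at a true proportion of 5%, 10% and 15%.

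**Step 7: price of ten tests.** If the tests are independent, the chance of at least one false positive is 1−(1−size)¹⁰.

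| Method | k=2 | k=3 | k=4 | k=5 |
|---|---|---|---|---|
| Exact rank-sum | 39% | 40% | 38% | 38% |
| Fisher, pre-fixed 16/16 | 0% | 0% | 0% | 36% |
| Fisher, five cuts searched | 0% | 50% | 58% | 63% |

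**Step 8: power.** For an assumed 1.0-SD shift in a normal, untied predictor (the documents give no effect size; 20,000 simulations per cell):
- exact rank-sum: 24%, 32%, 39%, 47%
- Fisher at 16/16: 0%, 0%, 0%, 32%
- Fisher with the 8 highest values as one group: 0%, 18%, 41%, 23%, but about 0% if the group is cut at the wrong end of the scale.

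**Step 9: ties.** Protocol 5.1.3 admits only participants with undetectable total HIV DNA, and protocol 4.2 requires viral load below 50 copies/ml. The tied share is not given. If all controllers lie among the tied lowest values, the exact rank-sum p (midranks) is:
- 16 of 32 tied: 0.37, 0.17, 0.08, 0.037
- 24 tied: 0.81, 0.56, 0.46, 0.30
- 28 tied: 1.0, 1.0, 0.82, 0.59.

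**The case against.** **Weight.** The analysis is exploratory, the shells are labelled as examples, and the n(%) heading over range cells looks like a template slip that SAP 3.3 lets the reader repair. At a true 5% there would more often than not be too few controllers to test anything, and rank-sum power is modest even at a 1-SD shift. All of this stands and limits the point. It does not supply a test for ten rows that carry a p-value column.

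**Existing safeguards.** The SAP introduction requires major changes of method to be described and justified in the report, which discourages a silent choice but fixes no cut. The Cox models take the same ten variables without levels and use every rebound event, so they may well be the more informative predictor analysis. Their outcome is time to rebound, so they cannot fill the odds-ratio column of Example Table 6.

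**Remedy.** Stated cut-points, or a named exact or penalised logistic model, would also close the gap and would keep an odds ratio. That is fair. The rank-sum test is preferred because it needs neither a cut nor a unit of increase. The exact Hodges-Lehmann interval assumes untied data, so it should not be used for heavily tied predictors. That objection stands, and the fix is limited accordingly.

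**Stronger readings a reader might infer.**
- That Fisher's test can never reach 5% with 2 to 4 controllers. It can at uneven cuts; the limit in Step 3 belongs to the median cut.
- That the plan intends to search for a cut, or that false positives are inflated whenever one does. The documents say neither. The size depends on which cuts are tried, and it is 0% with 2 controllers for the five used here.
- That the trial's main conclusion is at risk. The primary proportion and its Wilson interval do not use this table.

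**Conclusion.** The concern holds as a gap in the exploratory analysis. The one test named in SAP 4.3 and protocol 8.3.4 cannot be run on ten of the twelve rows of Example Table 6 without a cut-point that the plan does not give. The odds ratio in those rows has no model, and their headings contradict their cells.

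The consequence is that an unstated choice controls the result. A median cut rules out p<0.05 with 2 to 4 controllers, while a searched cut can push the per-predictor error above 5% with 3 to 5 controllers. These figures assume 32 complete participants, two-sided tests, untied predictors and illustrative cuts. The familywise figures also assume independence, and the power figures assume a 1.0-SD shift.

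It should be corrected before database lock. It does not touch the primary endpoint.

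**What to change.** Change SAP 4.3 and Example Table 6, and note in the SAP any departure from protocol 8.3.4. Protocol section 8 leaves the analysis to a SAP approved before database lock, so a protocol edit is not needed for this exploratory analysis.

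1. Keep Fisher's exact test for gender and for age as categorised.
2. Test the other ten predictors undichotomised with the exact permutation Wilcoxon rank-sum test, with midranks for ties.
3. In those ten rows show median (IQR) by group under a corrected heading.
4. In place of the odds ratio, give a Hodges-Lehmann difference with exact 95% CI only for largely untied predictors. For predictors heavily tied at a detection limit or on a dilution scale, give only the descriptive summary and the permutation p-value. These are baseline reservoir, viral load (unless the ultrasensitive assay in SAP 2.3 separates values) and possibly viral outgrowth, which protocol 5.3 measures in a 5-fold dilution series.
5. With 0 or 1 controllers, run no test of control and rely on the planned Cox models for time to rebound.
6. State the limits: ten unadjusted tests of size near 5% carry up to about a 40% chance of at least one false positive if independent, so p-values are hypothesis-generating; power stays limited; and little is gained for heavily tied predictors.

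The cost is SAP wording and one table shell, with no extra data and standard software. The real price is statistical: with 2 to 4 controllers the familywise false-positive chance is higher than under a pre-fixed median cut (38% to 40% against 0%), which is why item 6 belongs in the text.
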